6.5 Accrual Rate

1-2 participants per month

6.6 Length of Study

16-20 months

7.0 Data Management

Informed consent document	EPIC
Protocol Eligibility Form	
Protocol Registration Form (Appendix B)	ORIS
Race and Ethnicity Verification Form	
Clinical Evaluation from History/Exam (Appendix D)	REDCap
Exploratory Outcome Data Collection Form (Appendix E)	REDCap
EORTC QLQ-CIPN20 (neuropathy scale) (Appendix F)	REDCap
Nerve Fiber Density Data Collection Form (Appendix G)	REDCap
Ultrasound Nerve Diameter Data Form (Appendix H)	REDCap

Nerve Conduction Study Data Collection Form (Appendix I)	REDCap
Adverse Events Log (Appendix J)	ORIS

8.0 Confidentiality and Privacy

Confidentiality will be protected by collecting only information needed to assess study outcomes, minimizing to the fullest extent possible the collection of any information that could directly identify subjects, and maintaining all study information in a secure manner. To help ensure subject privacy and confidentiality, only a unique study identifier will appear on the data collection form. Any collected patient identifying information corresponding to the unique study identifier will be maintained on a linkage file, store separately from the data. The linkage file will be kept secure, with access limited to designated study personnel. Following data collection subject identifying information will be destroyed (state the anticipated time the data will be destroyed, e.g. three years after closure of the study, and the method of destruction), consistent with data validation and study design, producing an anonymous analytical data set. Data access will be limited to study staff. Data and records will be kept locked and secured, with any computer data password protected. No reference to any individual participant will appear in reports, presentations, or publications that may arise from the study.

9.0 Data Safety and Monitoring

The principal investigator will be responsible for the overall monitoring of the data and safety of study participants. The principal investigator will be assisted by other members of the study staff.

10.0 Reporting of Unanticipated Problems, Adverse Events or Deviations

Any unanticipated problems, serious and unexpected adverse events, deviations or protocol changes will be promptly reported by the principal investigator or designated member of the research team to the IRB and sponsor or appropriate government agency if appropriate.

Adverse events will be tracked for 30 days following skin biopsy. This time is adequate to evaluate for potential adverse events from this and all study procedures. Adverse events will not be tracked beyond 30 days following the neurodiagnostic and skin biopsy procedures unless a delayed event is felt to be related to the study intervention.

References

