4.2 Study Activities

Study Calendar*				
	Encounter 1	Encounter 2	Encounter 3	Follow-up: 30 days to confirm adequate healing of biopsy
Informed Consent	X			
Medical history (Appendix C)		X		
Physical exam		X		
QLQ-CIPN20 ^f		X		
Blood draw ^{c,f}		X		
Abbreviated Neurologic Exam ^a			X	
Nerve Conduction Study ^b			X	
Ultrasound ^d			X	
Skin Biopsies ^e			X	
Follow-up skin assessment				X

* The Study Calendar represents an ideal schedule for the completion of study related activities; however, depending on patient and physician availability, the completion of these clinical tasks may occur at any clinical encounter. ***The exceptions to this rule are following: the informed consent should be signed before any research activity occurs, and the blood draw and the QLQ-CPIN20 should be performed on the same day. While all study related tasks may be completed at a single visit, it is anticipated that due to scheduling, at least 2 study visits will be required.

a: exam to include strength assessment of the tibialis anterior and gastrocnemius and deep tendon reflex exam of the Achilles on the limb to be examined with NCV and US.

b: Sural and Tibial nerve assessments

c: Green top heparin tube: 12 ml blood sample

d: Sural and Tibial nerve assessments

e: Two skin biopsies will be obtained as 4mm punch biopsies at distal end of leg in sural nerve territory (10cm above lateral malleolus) and from the thigh

f: The blood draw and the QLQ-CIPN20 should be performed on the same day.

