4.7 Follow-up

Results of diagnostic testing will be made available in the participant's medical record. If unexpected abnormalities are detected, the primary oncologist will be contacted and a Neurology referral can be placed as part of the patient's routine clinical care. The patient will also be followed for 30 days to ensure the biopsy site is healing adequately. This follow up may be by telephone or in person.

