Appendix K: Follow-up Form for Skin Biopsy

ORIS PID: _____	Date Completed: ___/___/___
PI: [name]., [name]. Study Number: CCCWFU 97217	

Date of Skin Biopsy	Phone / In-person assessment completed within 30 days (circle one)	Any skin biopsy problems reported by participant?
___/___/___	Yes / No	
___/___/___		Yes / No

A Pilot Study Using Ultrasound for the Detection of Taxane-Induced Peripheral
Neuropathy
Wake Forest Baptist Comprehensive Cancer Center (WFBCCC)
CCCWFU # 97217

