A Pilot Study Using Ultrasound for the Detection of Taxane-Induced Peripheral
Neuropathy
Wake Forest Baptist Comprehensive Cancer Center (WFBCCC)
CCCWFU # 97217

What is considered an SAE under this mandatory procedure?

Any **unexpected grade 4** event and **all grade 5 events** (death during protocol intervention) should be reported. These events should be reported if they occur while a patient is on study treatment or if they occur within 30 days of last study treatment (even if patient begins a new treatment during the 30 days). This window of 30 days should be the standard window to be used in all protocols unless a specific scientific rationale is presented to suggest that a shorter window can be used to identify events. In addition, if it is not clear whether the Grade 4 is unexpected it should be reported.

Table 1: Summary of STRC Reporting Requirements for Institutional Pilot, Phase 1, Phase 2 and Phase 3 Interventional Trials

STRC reporting may not be appropriate for specific expected adverse events for protocols. In those situations the adverse events that will not require STRC reporting **must be specified in the text of the approved protocol.**

	ADVERSE EVENT					
	Grade 1, Grade 2, Grade 3		Grade 4		Grade 5	
	Unexpected	Expected	Unexpected	Expected	Unexpected	Expected
Unrelated	Not Required	Not Required	REPORT TO STRC	Not Required	REPORT TO STRC	REPORT TO STRC
Unlikely	Not Required	Not Required	REPORT TO STRC	Not Required	REPORT TO STRC	REPORT TO STRC
Possible	Not Required	Not Required	REPORT TO STRC	Not Required	REPORT TO STRC	REPORT TO STRC
Probable	Not Required	Not Required	REPORT TO STRC	Not Required	REPORT TO STRC	REPORT TO STRC
Definite	Not Required	Not Required	REPORT TO STRC	Not Required	REPORT TO STRC	REPORT TO STRC

STRC notification responsibilities of the person handling the reporting/documenting of the SAE:

1. Make a phone call (or speak in person) to the appropriate clinical member of the STRC as listed below (page if necessary)—see note 2 below
2. Submit the STRC Notification Form **WITHIN 24 HOURS** of first knowledge of the event. This form is found at either the ORIS main menu page or by going to <http://ccc.wfubmc.edu/oris/strc.aspx>.
This will ensure that all persons that need to be made aware of the event (i.e., study team members and STRC members) will be notified; remember to file a copy of your

A Pilot Study Using Ultrasound for the Detection of Taxane-Induced Peripheral
Neuropathy

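### Section 10 claims that 30 days of tracking after the biopsy covers all study procedures, but it sets no start, never names the blood draw, and Appendix K accepts a single early contact about the biopsy alone

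*Combined protocol and SAP*

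**What the plan says.** Section 10.0 sets the tracking period: "Adverse events will be tracked for 30 days following skin biopsy". It then asserts the reach of that period: "This time is adequate to evaluate for potential adverse events from this and all study procedures". The next sentence closes tracking by a different event and adds an exception: "Adverse events will not be tracked beyond 30 days following the neurodiagnostic and skin biopsy procedures unless a delayed event is felt to be related". The opening paragraph of the same section has a separate rule with no time limit: "Any unanticipated problems, serious and unexpected adverse events, deviations or protocol changes will be promptly reported".

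The study calendar (Section 4.2) puts the blood draw at Encounter 2 and the neurological exam, nerve conduction study, ultrasound and biopsies at Encounter 3. It treats this order as an ideal, since "the completion of these clinical tasks may occur at any clinical encounter", and expects at least two visits. Section 4.6 has the Encounter 3 tests done at one visit.

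On follow-up, Section 4.7 says "The patient will also be followed for 30 days to ensure the biopsy site is healing adequately", by telephone or in person, and the calendar's last column is a 30-day follow-up of biopsy healing. Appendix K records "Phone / In-person assessment completed within 30 days (circle one", and its only question is whether the participant reported a skin biopsy problem. The log in Appendix J has bruising, dizziness and syncope already printed as event terms.

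**The concern.** Two statements about safety ascertainment do not match the procedures and the form meant to deliver them.

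First, a period that opens at the biopsy cannot capture an event from a blood draw at an earlier visit. Bruising, dizziness and syncope are plausible after venepuncture, and the study's own log anticipates them.

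Second, the protocol body describes a 30-day follow-up, whereas the form asks for one contact at any time within those 30 days. If that contact comes early, no later contact is scheduled at which a new biopsy problem would be asked about. The form does not ask about the other procedures at all.

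What is at stake is whether a report can say that adverse events from all study procedures were looked for over 30 days.

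**Working it through.** The plan gives no figure to reproduce here. The check sets the passages side by side, with day counts as illustration. Visit spacing and contact day are assumptions, because the documents give neither.

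**1. Start of collection.** Section 10 names no start other than the biopsy. In the calendar's ideal order the draw (Encounter 2) precedes the biopsy (Encounter 3). If the gap is g days, the g days from the draw to the biopsy lie before the only stated period opens: 0 days if g = 0, 7 if g = 7, 14 if g = 14. The exception for delayed related events extends the end of tracking, so it does not reach back to these days. A patient who has the draw but never the biopsy has no stated period.

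**2. End of collection.** One sentence in Section 10 counts 30 days from the biopsy; another counts from the neurodiagnostic procedures and the biopsy. If all Encounter 3 tests fall on one day, as Section 4.6 plans, the two ends coincide. If the calendar's flexibility is used and the neurodiagnostic tests come g days after the biopsy, the ends are day 30 and day 30 + g; with g = 14, day 30 and day 44. Neither sentence names the blood draw. If the draw comes g days after the biopsy, a biopsy-only period leaves it max(0, 30 − g) days of cover: 23 for g = 7, 16 for g = 14, 0 for g = 30.

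**3. The follow-up form.** Appendix K sets a latest day for the contact but no earliest day. For a single contact on day c, the days with no later scheduled contact are 30 − c:

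| Assumed contact day | Days left | Share of 30 |
|---|---|---|
| 7 | 23 | 77% |
| 14 | 16 | 53% |
| 21 | 9 | 30% |
| 30 | 0 | 0% |

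Each row satisfies the form's completion item. Only the last spans the 30 days in Section 4.7 and the calendar.

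**4. What is still caught.** Serious and unexpected events and unanticipated problems are reportable without a time limit. Delayed events judged related are excepted from the cut-off. Both routes depend on the study team learning of the event. What drops out is mainly the non-serious event nobody asked about: one after a draw that precedes the biopsy, or a biopsy problem arising after an early contact.

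**5. Best case.** If every procedure is done on one day and the contact is made on day 30, there is no timing gap. The form would still ask only about the biopsy.

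**The case against.** The strongest reply is that the practical gap is small, and much of that stands. Section 4.5 says that in most cases the study sample is added to routine phlebotomy, so often the study causes no extra venepuncture; only some participants need a further draw. Section 4.6 puts the neurodiagnostic tests and the biopsy at one visit, so the uncovered procedure is mainly the blood draw. The log in Appendix J has a start-date column and no instruction to leave out events before the biopsy. No objective or planned analysis concerns safety. None of this supplies a start of collection or makes the claim about all procedures true as written.

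A reader might go further in four ways that the documents do not support.

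- *That tracking runs from the biopsy alone.* Section 10 also ties the end to the neurodiagnostic procedures. The defect is two end anchors and no stated start.
- *That a patient contacted early counts as fully followed.* No section defines complete follow-up by Appendix K, and Section 4.7 and the calendar still give 30 days. The form also carries a completion date and the biopsy date, from which an early contact might be seen. Its table did not survive text extraction well, so its layout should be read with caution.
- *That most of the 22 patients have uncovered study exposure.* The calendar's expectation of at least two visits counts visits, not study-caused draws, and it also allows everything at one visit.
- *That Appendix L gives conflicting reporting clocks.* Its period covers events "if they occur within 30 days of last study treatment", and this study gives no treatment. But the appendix is a general institutional procedure whose definitions limit interventional trials to two therapeutic levels, so its application here is unclear. Nothing shows that staff would count from chemotherapy. The treatment-related columns in Appendix J look like template remnants.

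**Conclusion.** The point holds as a limited inconsistency in safety ascertainment. Section 10 claims coverage of all study procedures for a period with no stated start, two end anchors and no mention of the blood draw. Appendix K can be completed by one early contact confined to the biopsy, although Section 4.7 and the calendar state 30 days.

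The size cannot be estimated from the documents. It runs from no timing gap (one visit, contact on day 30) to the days shown in the working, which rest on assumed visit gaps and contact days. The loss is mainly of non-serious events and of active ascertainment. The CSA comparison, its sample size and its power do not depend on any of this. The correction is still worth making because it is cheap and the coverage statement is otherwise untrue when the plan is followed as written.

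**What to change.** - **Section 10.0:** start adverse-event collection at the first study procedure and use one end anchor that covers every study procedure, with the blood draw named. Otherwise, drop the statement that the biopsy period is adequate for all procedures.
- **Appendix K:** reconcile it with Section 4.7 and the calendar, so that the form shows the day of contact, shows whether the stated 30-day period was covered, and asks about all study procedures.

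The clinical follow-up schedule, including when contacts are made, is for the sponsor to decide; the request is only that these passages agree.

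The cost is wording in one section and one form. The downside is that some contacts may be made later than they would have been and a few more minor events will be logged.

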Appendix A: Subject Eligibility Checklist

IRB Protocol No. 00043631	CCCWFU Protocol No. 97217
Study Title: A Pilot Study Using Ultrasound for the Detection of Taxane-Induced Peripheral Neuropathy	
Principal Investigators: [name]., [name]	

Inclusion Criteria (as outlined in study protocol)	Criteria is met	Criteria is NOT met	Source Used to Confirm * (Please document dates and lab results)
Breast cancer (any stage).			
Previously or currently receiving taxane-based chemotherapy			
Clinical symptoms of peripheral neuropathy noted in medical record			
Ability and willingness to understand and sign an informed consent			
Exclusion Criteria (as outlined in study protocol)	Criteria NOT present	Criteria is present	Source Used to Confirm * (Please document dates and lab results)
Self-reported or documented history of pre-existing peripheral neuropathy prior to initiation of taxane chemotherapy			
Unable to provide history			
Male patients			

This subject is eligible / ineligible for participation in this study.

ORIS Assigned PID: _____

Signature of research professional confirming eligibility: _____

Date: ___/___/___

Signature of Treating Physician: _____ Date: ___/___/___

Signature of Principal Investigator**: _____ Date: ___/___/___

* Examples of source documents include clinic note, pathology report, laboratory results, etc. When listing the source, specifically state which document in the medical record was used to assess eligibility. Also include the date on the document. Example: "Pathology report, 01/01/14" or "Clinic note, 01/01/14"

**Principal Investigator signature can be obtained following registration if needed

Appendix B: Protocol Registration Form

DEMOGRAPHICS

Patient: Last Name: _____ First Name: _____

MRN: _____ DOB (mm/dd/yy): ____ / ____ / ____

ZIPCODE: _____

SEX: Male Female

Ethnicity (choose one): Hispanic
 Non-Hispanic

Race (choose all that apply): WHITE BLACK ASIAN

PACIFIC ISLANDER NATIVE AMERICAN

Height: ____ . ____ inches Weight: ____ . ____ lbs.(actual)

Surface Area: ____ . ____ m² BMI: ____ . ____ kg/m²

Primary Diagnosis: _____

Date of Diagnosis: ____ / ____ / ____

Performance Status: ____ ECOG Karnofsky

PROTOCOL INFORMATION

Date of Registration: ____ / ____ / ____

MD Name (last) : _____

Date protocol treatment started: ____ / ____ / ____

Informed written consent: YES NO

(consent must be signed prior to registration)

Date Consent Signed: ____ / ____ / ____

PID # (to be assigned by ORIS): _____

Protocol Registrar can be contact by calling [contact] between 8:30 AM and 4:00 PM, Monday – Friday.

Completed Eligibility Checklist and Protocol Registration Form must be hand delivered, faxed or e-mailed to the registrar at [name] or [contact].

Appendix C - Race & Ethnicity Verification Form

Thank you so much for helping us to verify your race and ethnicity to ensure the quality of our information. As a brief reminder, the information you provide today will be kept confidential.

1. Are you:
 - Hispanic or Latino/a
 - Not Hispanic or Latino/a

2. What is your race? One or more categories may be selected.
 - White or Caucasian
 - Black or African American
 - American Indian or Alaskan Native
 - Asian
 - Native Hawaiian or Other Pacific Islander
 - Other, Please Specify: _____

Internal use only:

Name: _____ MRN#: _____

Was the self-reported race and ethnicity of the participant verified at the time of consent?

Yes **No**

Was a discrepancy found? **Yes** **No**

If yes, please provide what is currently indicated in the EMR:

Ethnicity: _____ Race: _____

Additional comments: _____

A Pilot Study Using Ultrasound for the Detection of Taxane-Induced Peripheral
Neuropathy
Wake Forest Baptist Comprehensive Cancer Center (WFBCCC)
CCCWFU # 97217

Appendix D: Clinical Evaluation from History/Exam

ORIS PID: _____	Date Completed: ___ / ___ / ___
PI: [name]., [name]. Study Number: CCCWFU 97217	
Instructions: To be filled out by medical staff.	

1. Oncologic history
Diagnosis and stage: _____

a. Most immediate prior cancer therapy (select one):
 chemotherapy radiation surgery hormone other:

b. Specify most immediate prior taxane chemotherapy:

Dates of administration: Started: ___ / ___ / ___ Stopped: ___ / ___ / ___

Dose _____ & total # of treatments _____

c. Other prior cancer therapies (excluding 1b.) for most recent cancer. Mark all that apply:
 None Chemotherapy Radiation Surgery Hormone therapy Other:

Regimen Name	Total # of Treatments	Date of Last Treatment, or 'ongoing' for certain HT
1.		___ / ___ / ___
2.		___ / ___ / ___
3.		___ / ___ / ___
4.		___ / ___ / ___
5.		___ / ___ / ___
6.		___ / ___ / ___
7.		___ / ___ / ___
8.		___ / ___ / ___
9.		___ / ___ / ___
10.		___ / ___ / ___

Site of RT	Total Dose in Gy	Date of Last Treatment
1.		___ / ___ / ___
2.		___ / ___ / ___
3.		___ / ___ / ___
4.		___ / ___ / ___
5.		___ / ___ / ___

Type of surgery	Date of surgery
1.	___ / ___ / ___
2.	___ / ___ / ___

A Pilot Study Using Ultrasound for the Detection of Taxane-Induced Peripheral
Neuropathy
Wake Forest Baptist Comprehensive Cancer Center (WFBCCC)
CCCWFU # 97217

Hormone Therapy Name	Dose	Date of Last Treatment
1.		___/___/___
2.		___/___/___

Other	Dose	Date of Last Treatment
1.		___/___/___
2.		___/___/___

2. Medical history (check all that apply):

- Thyroid Disorder
- Hyperthyroidism Hypothyroidism
- Vitamin B12 deficiency
- Peripheral vascular disease (claudication, arterial bypass, untreated aneurysm (≥6cm))
- Cerebrovascular disease (history of TIA or CVA)
- Alcoholism
- Carpal tunnel syndrome
- Sciatica
- Diabetes
end organ damage? Yes No
- AIDS
- Depression
- Other major medical condition; specify

4. Concurrent medications and supplements

a. List all prescription and over-the-counter medications (includes prescription supplements)

Medication Name	Is it PRN?	Medication Name	Is it PRN?
1.	yes no	11.	yes no
2.	yes no	12.	yes no
3.	yes no	13.	yes no
4.	yes no	14.	yes no
5.	yes no	15.	yes no
6.	yes no	16.	yes no
7.	yes no	17.	yes no
8.	yes no	18.	yes no

A Pilot Study Using Ultrasound for the Detection of Taxane-Induced Peripheral
Neuropathy
Wake Forest Baptist Comprehensive Cancer Center (WFBCCC)
CCCWFU # 97217

9.	yes no	19.	yes no
10.	yes no	20.	yes no

b. List all supplements (excludes prescription supplements)

Supplement Name	Is it PRN?	Supplement Name	Is it PRN?
1.	yes no	11.	yes no
2.	yes no	12.	yes no
3.	yes no	13.	yes no
4.	yes no	14.	yes no
5.	yes no	15.	yes no
6.	yes no	16.	yes no
7.	yes no	17.	yes no
8.	yes no	18.	yes no
9.	yes no	19.	yes no
10.	yes no	20.	yes no

5. Physical exam:

- Derm – WNL Abnormal, specify _____
- HEENT – WNL Abnormal, specify _____
- CV – WNL Abnormal, specify _____
- Pulm – WNL Abnormal, specify _____
- GI – WNL Abnormal, specify _____
- Other – Abnormal, specify _____

A Pilot Study Using Ultrasound for the Detection of Taxane-Induced Peripheral Neuropathy
 Wake Forest Baptist Comprehensive Cancer Center (WFBCCC)
 CCCWFU # 97217

Appendix E: Exploratory Outcomes Data Collection Form

ORIS PID: _____	Date Completed: ___ / ___ / ___
PI: [name]., [name]. Study Number: CCCWFU 97217	

Instructions

- Use the ORIS PID to Identify the Sample
- Date is the date of experimentation
- Target Name (Serum Outcomes): Name of the target of the assay
- Record amounts to 3 decimal places (serum outcomes)
- Initials of person performing the assay.

*Do not erase entries. If an entry is incorrect, cross the entry out, initial, and write in the correct entry. Please write neatly.

Exploratory Outcomes Data Form							
Date of blood sample collection	Serum Outcomes			IHC and Positive Cell Count			
	Target Name	Amount (ng/ml)	Initials	Mast Cell Number	Tryptase	Chymase	Histamine
___/___/___							

A Pilot Study Using Ultrasound for the Detection of Taxane-Induced Peripheral
Neuropathy
Wake Forest Baptist Comprehensive Cancer Center (WFBCCC)
CCCWFU # 97217

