Two skin biopsies will be obtained as 4-5mm punch biopsies at distal end of leg in sural nerve territory (10cm above lateral malleolus) and in the upper thigh. As described in a review by Lauria and Devigili (2007),³¹ biopsied tissue will be cut into 50 uM sections which will be hematoxylin and eosin stained and also immunostained with an antibody to PGP (protein gene product) 9.5, a neuron- and neuroendocrine cell-specific ubiquitin carboxy-terminal hydrolase expressed throughout the peripheral nervous system. Slides will be reviewed by Dermatopathology ([name] and/or [name]) in order to count PGP9.5-positive fibers as they cross the dermal-epidermal junction to calculate linear density of IENF (IENF/mm). Additional staining will be done as indicated. Routine processing of specimens and comparison to standardized values (similar to those described by McArthur et al.(1998))²⁵ will be done by Dermatopathology as per their institutional guidelines. These methods are standard clinical procedures for the routine assessment of IENF density. Dermatopathology will also obtain descriptive measures of morphologic changes that will be analyzed as an exploratory outcome. Additional unstained slides or blocks will be stored and transferred to [name] lab for staining and testing of mast cell concentration, tryptase, chymase and histamine. The results will be recorded on Appendix E for transfer into REDCap.

Storage of Serum and Skin Biopsy Material

Venous blood will be stored in lab refrigerator prior to transfer (in oncology lab) and after transfer (in [name] lab). Serum and left over skin biopsy material from patients will be stored in [name] laboratory in the Department of Cancer Biology until use.

Tests Using Serum

Serum testing for inflammatory markers will be performed using commercially available kit that may include but not be limited to ELISA and will be performed according to the

manufacturers' instructions and modified accordingly if needed given the type of sample and/or target of interest to be detected. Data resulting from these experiments may be kept in laboratory notebooks or in on the data sheets provided in Appendix C.

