5.3 Exploratory Outcome

5.3.1 The number of activated mast cells (per mm) in TIPN patients

5.3.2 Serum levels of inflammatory molecules in TIPN patients chosen at the investigators discretion

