5.4.6 Use of analgesics or treatments for neuropathy

5.4.7 History of clinically documented compressive neuropathy (carpal tunnel syndrome)

6.0 Analytic Plan

6.1 Sample Size and Power

6.1.1 Primary outcome:

This current study will enroll a sample size of 22 in TIPN patients to compare to historical data that was previously collected from 60 healthy patients. Using a two-sided test and significance level of 0.05, we will have an 80% power to detect an effect size of 0.73 (unit: standard deviation [SD]) when comparing TIPN patients to that historical data. We have permission to utilize historical data (primary data) collected from healthy patients which found that the mean and SD of the tibial nerve CSA were 14.2 and 4.4 mm², respectively (published by Cartwright et al., 2008). Assuming the same SD in TIPN patients, we will have more than 80% power to detect a difference of 3.2 mm² for the tibial nerve. Based on Riazi et al. (2012),³² the mean increase in size of tibial nerve was 5.3 when comparing subjects with diabetic sensorimotor polyneuropathy and control subjects. Even though the study sample is not exactly the same, with the minimal detectable difference equal to 3.2, we should have sufficient power for this analysis.

6.1.2 Secondary outcome:

In historical data collected from healthy patients (Cartwright et al., 2008),⁸ the mean and standard deviation (SD) of the sural nerve CSA were 5.3 and 1.8 mm², respectively. Assuming the same SDs in TIPN patients, we will have more than

80% power to detect a detectable difference of 1.3 mm² for the sural nerve between TIPN patients and healthy patients.

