6.4 Analyses of Exploratory Outcomes

Spearman's rank correlation coefficient will be used to assess the associations between activated mast cells in skin biopsies, serum inflammatory markers, severity of symptoms, and primary outcome and secondary outcomes in TIPN patients.

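### Appendix E records every serum marker in ng/ml to three decimals (a 1 pg/ml step) before markers or kits are chosen, which could blunt the exploratory rank correlations for a very low-concentration marker.

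*Combined protocol and SAP*

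**What the plan says.** Appendix E is the collection form for the exploratory outcomes. Its instruction for serum results is "Record amounts to 3 decimal places (serum outcomes"), and its single serum amount column is headed in ng/ml. The serum part otherwise asks only for the sample date, the target name and initials. There is no unit column, no detection-limit field and no instruction for an undetectable result.

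Section 7.0 lists the "Exploratory Outcome Data Collection Form (Appendix E") with REDCap as its destination.

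The targets are open. Section 5.3.2 defines the outcome as "Serum levels of inflammatory molecules in TIPN patients chosen at the investigators discretion". The assay is open too. Section 4.6 says "Serum testing for inflammatory markers will be performed using commercially available kit that may include but not be limited to ELISA", and allows the method to be modified for the sample or target.

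Section 4.6 also says "Data resulting from these experiments may be kept in laboratory notebooks or in on the data sheets provided in Appendix C".

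For the analysis, section 6.4 states "Spearman's rank correlation coefficient will be used to assess the associations between activated mast cells in skin biopsies, serum inflammatory markers", together with symptom severity and the primary and secondary outcomes. It gives no test level or power.

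**The concern.** The form fixes the resolution of the data before anyone has decided what will be measured. One unit and one rounding rule cannot be known to suit markers that are not yet named. Where a marker's values are of the same order as the 1 pg/ml step, patients with different readings receive the same recorded value.

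Spearman's coefficient uses only the ordering of the values, so these ties remove the information that the planned analysis depends on. A reading below 0.5 pg/ml becomes 0.000. An undetectable result has no other numeric entry available, so the two may become indistinguishable. At stake is sensitivity to a real association in a small exploratory analysis. No primary or secondary outcome is involved.

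**Working it through.** The plan states no power, error rate or expected level for the serum markers, so there is no figure of its own to reproduce.

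**Inputs from the documents**
- Unit ng/ml and three decimals (Appendix E).
- Spearman correlation (section 6.4).
- n = 22: "This current study will enroll a sample size of 22 in TIPN patients" (section 6.1.1).
- Test level: "Using a two-sided test and significance level of 0.05" (section 6.1.1). It is stated for the primary outcome and borrowed here for illustration only.

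**Assumed inputs, not in the documents**
- The marker is lognormal with median m pg/ml and log-SD s.
- The correlation between the log marker and the other variable is 0.6.
- At first, the assay has no detection limit.

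**Step 1, resolution.** 0.001 ng/ml × 1000 pg/ng = 1 pg/ml. Readings below 0.5 pg/ml are recorded as 0.000, and readings from 0.5 to 1.5 pg/ml as 0.001.

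**Step 2, share at each recorded value.** P(0.000) = Φ[ln(0.5/m)/s] and P(0.001) = Φ[ln(1.5/m)/s] − Φ[ln(0.5/m)/s].
- m = 1, s = 0.6: P(0.000) = Φ(−1.155) = 0.12, and P(0.001) = Φ(0.676) − 0.12 = 0.75 − 0.12 = 0.63.
- m = 0.5, any s: P(0.000) = Φ(0) = 0.50.
- m = 0.3, s = 0.6: P(0.000) = Φ(0.851) = 0.80.

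**Step 3, effect of spread at a median of 1 pg/ml** (simulation, n = 22, 4,000 runs per setting). Without rounding, mean rho is about 0.56 and power about 82%.

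| log-SD | distinct values (mean) | at 0.000 | at 0.001 | mean rho | power |
|---|---|---|---|---|---|
| 0.3 | 2.1 | 1% | 90% | 0.35 | 33% |
| 0.5 | 3.4 | 8% | 71% | 0.47 | 65% |
| 0.7 | 4.4 | 16% | 56% | 0.52 | 74% |
| 1.0 | 5.6 | 24% | 41% | 0.54 | 78% |

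At log-SD 0.3, about 10% of samples have a single recorded value, so rho cannot be computed.

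**Step 4, effect of the median at log-SD 0.6.** Power without rounding is about 81 to 82%.

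| median, pg/ml | power on the form |
|---|---|
| 0.3 | about 48% |
| 0.5 | about 67% |
| 1 | about 72% |
| 2 | about 79% |
| 5 | no loss |

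**Step 5, add a detection limit.** The settings are those of step 4, with non-detects tied below the lowest detected value (3,000 runs).

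| median, pg/ml | detection limit, pg/ml | power, all digits kept | power on the form |
|---|---|---|---|
| 0.3 | 0.5 | 50% | 49% |
| 0.5 | 0.5 | 74% | 68% |
| 0.5 | 1 | 36% | 37% |
| 1 | 0.5 | 81% | 73% |
| 1 | 1 | 75% | 73% |

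The Monte Carlo standard error is about √(0.73 × 0.27/3000) = 0.8 points, so gaps of one or two points between runs carry no meaning.

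**The case against.** The strongest objection is that steps 3 and 4 assume an assay with no detection limit, even at a median of 0.3 pg/ml. Step 5 shows how much rests on that. With a limit of 0.5 pg/ml, the largest loss in step 4 is almost entirely the kit's and not the form's. This stands. The form itself costs something noticeable only when the kit reads below about 1 pg/ml: roughly 6 to 8 points in the step 5 settings with a limit of 0.5 pg/ml and a median of 0.5 or 1.

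Second, nothing in the documents places any marker at these levels, and from about 5 pg/ml upward the rounding hardly matters. This also stands, and makes the point conditional.

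Third, section 4.6 lets results be kept in laboratory notebooks, and rounding on a form does not erase the assay reading. A reader might infer that the form destroys data, or that the 12 ml draw would rule out recovery. The documents do not support that, because unrounded readings may exist and correcting an entry needs no more blood. The notebook is not a dependable safeguard, however. Its use is optional, nothing requires full-precision values to reach REDCap, and the data sheet named in that sentence, Appendix C, is the race and ethnicity form.

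Fourth, these are exploratory outcomes in a pilot with no decision rule. That limits the importance of the point but does not argue against a free correction.

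**Conclusion.** The point holds in a limited form. Appendix E sets a 1 pg/ml step for markers not yet chosen and gives no way to mark a non-detect. If a chosen marker lies near or below about 1 pg/ml and the kit resolves well below that, the planned correlations lose power: about 9 or 10 points at a median of 1 pg/ml with log-SD 0.6, more with a narrower spread or a lower median, about 3 points at 2 pg/ml and none at 5 or more. These sizes rest on the assumed lognormal shape, correlation of 0.6 and borrowed test level.

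A reader might infer that a marker near 1 pg/ml would be recorded mostly as 0.000. The arithmetic does not support that: about 12% of values would be 0.000 at log-SD 0.6 (1 to 24% across the spreads examined), and the main tie is at 0.001. Half or more zeros need a median of about 0.5 pg/ml or lower. It would also be wrong to conclude that any of the study's serum results are in fact degraded, because the documents give neither marker levels nor detection limits. This is a minor improvement to an exploratory outcome.

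**What to change.** In Appendix E and the matching REDCap field, replace the fixed ng/ml, three-decimal rule with an instruction to record each result in the unit the assay reports, with every digit it reports. Add a unit column, a non-detect flag and a field for the assay's lower limit of detection. In section 6.4, state that non-detects for a marker are ranked together below its lowest detected value. When the form is edited, the Appendix C reference in the serum paragraph of section 4.6 should be reconciled with Appendix E.

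The cost is a form and database field edit. It needs no extra blood, assay or patient contact. If results have already been entered in rounded form, full-precision values can be re-entered wherever laboratory notebooks hold them.
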